9.3. Inclusion Criteria

- Any subject who currently has or who has had the Sophono implant (including those who have been explanted)
- Has or has had Sophono implant for 3 months or longer

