10.1. Schedule of Events

After proper administration and signing of the IC and Research Authorization Forms, all potential subjects will be assessed for study eligibility based on the Inclusion and Exclusion Criteria. Inclusion and Exclusions data as well as limited demographic information will be captured in the subject CRFs.

A ***retrospective review*** of the subject's medical chart will be performed to gather and report data on subject surgical history, reportable AEs from the time of implantation to time of chart review, previous QOL scores, and previous audiometric testing results for Alpha 2 and/or Alpha 2 MPO processors.

An ***in-office visit*** will be conducted with an ENT physician and Audiologist, ideally on the same day, where the following assessments will take place:

ENT Visit:

The ENT visit will consist of an examination of the ear and implant site for skin complications (according to the *Holger Skin Evaluation Index* in Table 2) or other potential AEs (see Section 12 for reportable AEs). The ENT Visit CRF will detail findings (such as erythema, scar, etc.) as well as complications (skin loss, infection, etc.). Any such complications will be recorded on an AE form.

Sophono system satisfaction and QOL questions shall also be administered to allow the subjects' perceived benefits to be assessed. The QOL assessment will be done using the APHAB Version A.

Table 2. Holger Skin Evaluation Index

The skin directly over the implant site will be evaluated on the Holger Skin Evaluation Index.

Holger Skin Evaluation Index
0 = No irritation. Epithelium debris removed if present.
1 = Slight redness, local treatment.
2 = Red and slightly moist tissue. No granuloma formation noted. Local treatment. Extra controls.
3 = Status as in 1 and 2 but local revision became necessary.
4 = Removal of skin-penetrating implant necessary due to infection.
R = Removed implant for reasons not related to skin problems.

Audiology Visit:

All audiometric testing equipment should be calibrated and tested to American National Standards Institute (ANSI) standards, in good repair and functioning well.

All tests should be performed in the order presented in Table 3. Subject will be blinded to processor order.

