An anticipated adverse event is defined as an AE, the nature, severity, or degree of incidence of which is known and identified in applicable product labeling, published literature or the Investigational Plan or Informed Consent.

Based on event reports through literature review (15-19) anticipated Surgical Related AE's possibly noted in the Operative Report during the retrospective medical chart review should be reported on the appropriate CRF. These events may include:

This document is electronically controlled. Printed copies are considered uncontrolled.

Confidential

Table 4. Surgical Related Adverse Events

Event
Excessive Bleeding
Rupture of Dura
Cerebrospinal Fluid (CSF) Leak
Anesthesia Related Complications

Anticipated Post-operative Related AE's possibly seen in the retrospective medical chart review or at the office visit and their reportability within the study may include:

Table 5. Post-Operative Related Adverse Events

Event	Reportable Criteria
Abscess	Requiring medical intervention
Bleeding	Requiring medical intervention
Dehiscence (at Incision Site)	Requiring medical intervention
Depilation (Loss of Hair at Implant Site)	Excessive or cosmetically bothersome
Hematoma	Requiring medical intervention
Hyperemia	Excessive or requiring medical intervention
Infection (i.e. Cellulitis, Bacterial, etc.)	Requiring medical intervention
Inflammation/Skin Irritation (Redness)	Holger 2, 3, 4
Numbness (Hypoesthesia)	Notable or bothersome to subject

This document is electronically controlled. Printed copies are considered uncontrolled.

Confidential

Pain (Local)	Prolonged surgical procedure pain or pain lasting more than 10 days
Pressure (at the Implant Site)	Feeling of pressure continuing after subject begins using the processor
Scarring	Abnormal or Hypertrophic
Skin Necrosis (Pressure)	Requiring medical intervention
Swelling	Continuing after subject begins using the processor

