13.3. Safety endpoint

Event rates, weighted for center, will be displayed together with their 95% confidence interval (95%CI); for each possible sub-group, analyses will be compared by means of a mixed Poisson model, with center included as random effect. In the presence of over dispersion, negative binomial regression will be used. Over dispersion will be assessed both with a goodness-of-fit test and a likelihood ratio test for $\alpha=0$. The incidence rate ratio (IRR) and 95%CI will be reported [IRR=rate group1 / rate group2]. The exposure time (days/months) will be computed from implantation to the date of the follow-up visit for each patient [(data end – data in)/30.4].

Specific events will be analyzed using survival analysis. The analysis will be supported by a Kaplan Meier curve indicating the number of patients at risk and comparison of curves will be done using the generalized Log-Rank Test where appropriate. The exposure time (months) will be computed from the date of the implantation to the date of the last available follow-up or date of event: [(data end – data in)/30.4].

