7.1.3 Analysis Set

The following subject set will be used for the analysis:

- The Full Analysis Set (FAS) includes **all** patients enrolled in the study who sign Patient Informed Consent and fulfill the inclusion and exclusion criteria. The FAS will be used to evaluate the primary safety endpoint.
- The Per Protocol Set (PPS) includes all patients enrolled in the study who sign Patient Informed Consent, fulfill the inclusion and exclusion criteria, and perform prospective activities. The PPS will be used to evaluate the primary effectiveness endpoint and secondary endpoints.

The following table shows how each population set will be used for analyses:

Table x – Analysis steps by population set

Population set	Baseline assessment*	Primary Safety Endpoints	Primary Effectiveness Endpoints	Secondary Endpoints
FAS	✓	✓		
PPS	✓		✓	✓

*According to the clinical study team, baseline assessment on PPS will only be performed after evaluating the difference in sample size of FAS and PPS.

For those patients who drop out of the study, the analyses will include all data up to the point of their last data collection.

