PTA (dB)	The PTA will be calculated as average of the derived audiogram Hz values. For the AC test all the available values at 250Hz, 500Hz, 1000Hz, 2000Hz, 3000Hz, 4000Hz and 8000Hz will be considered in the calculation. For the BC or Aided tests all the available values at 500Hz, 1000Hz, 2000Hz, 3000Hz and 4000Hz will be considered in the calculation. Missing or VT values will not be considered in the calculation.
Gain (dB) in the free-field pure tone audiology	Absolute difference between PTA values
Time to first AE (days)	Study Evaluation- First AE occurrence date ¹
Total time in hospital (days)	Discharge date – Admission date

¹ if more than one procedure or event, consider the date of the first one.

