7.8 Treatment Characteristics

Duration of **Device Exposure** will be measured for FAS and PPS, in days starting from the implant through and including the time of last evaluation: Duration of device exposure (days) = (Study evaluation/explant date – Procedure date). Extent of device exposure will be presented in a summary table and supporting data listing.

Table x - Device Exposure

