7.10.1 Primary endpoint

The primary safety endpoint is the proportion of AEs related to the Sophono implant or surgery, which will be assessed through retrospective surgical chart review and prospective ENT exam. The primary safety endpoint will be evaluated on FAS. The AEs used for this endpoint are according to Investigator's determination of the event's relatedness to the device or surgery.

Adverse Event rates will be displayed together with their 95% confidence interval (95%CI) overall, by site and by type of event.

A time to first Adverse Event will be performed using survival analysis. The analysis will be supported by a Kaplan Meier curve indicating the number of patients at risk and any possible comparison of curves between groups will be done using the Log-Rank Test where appropriate.

Table x - Primary safety endpoint – Sophono Implant related Adverse Events rates

Figure x - Kaplan Meier estimate of first Sophono Implant related Adverse Event occurrence

Table x - Kaplan Meier estimate of first Sophono Implant related Adverse Event occurrence

The primary effectiveness endpoint is the absolute difference (gain) in the free-field pure tone audiometry assessed by PTA unaided (AC) and aided by the Alpha 2 MPO processor. The primary effectiveness endpoint will be evaluated on PPS.

The difference between unaided and aided measurements will be analyzed by means of paired (samples) t-test or Wilcoxon signed rank sum test according to the normal or non-normal distribution.

Additional analysis will be performed on:

- the "within indication" subset will exclude from the analysis subjects whose Prospective AC & BC tests do not meet the device indications for use.

- The subsets defined by implanted ear diagnosis. For the subject affected by SSD, analyses will be performed for both the derived variables (both NR substitution methods).

Table x - Primary effectiveness endpoint - Difference in PTA between unaided (AC) and aided by the alpha 2 MPO Processor (Audiogram Results Gain)

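### Subjects explanted before 3 months are outside the primary safety set although adverse events are counted from implantation, and the safety endpoint does not state that it is conditional on 3 months' retention

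*Protocol*

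**What the plan says.** - **Eligibility.** Protocol 9.3 requires that the subject "Has or has had Sophono implant for 3 months or longer"; the synopsis has the same rule. Protocol 9.2 makes all inclusion criteria mandatory, so the criterion that admits explanted subjects does not override the 3-month one.
- **Safety set.** SAP 7.1.3 assigns primary safety to the FAS, defined as "patients enrolled in the study who sign Patient Informed Consent and fulfill the inclusion and exclusion criteria. The FAS will be used to evaluate" (quote cut before the endpoint is named).
- **Event window.** Protocol 10.1 collects "reportable AEs from the time of implantation to time of chart review". Protocol 12.1.1 adds that anticipated surgical events "possibly noted in the Operative Report during the retrospective medical chart review should be reported on the appropriate CRF"; its Table 4 includes dural rupture and CSF leak.
- **Clock.** Protocol 13.3, for the survival analysis: "The exposure time (months) will be computed from the date of the implantation". SAP 7.8 measures device exposure "in days starting from the implant through and including the time of last evaluation".
- **Endpoint.** SAP 7.10.1: "The primary safety endpoint is the proportion of AEs related to the Sophono implant or surgery". A Kaplan-Meier analysis of the first event is planned, with no landmark or delayed entry.
- **Nearest thing to a label.** Protocol 5.1 and SAP 3 describe the aim as long-term outcomes, safety among them, in subjects with at least three months of implant duration. Protocol 6.1.1 and 6.2.1.1 and SAP 4.1 and 7.10.1 do not repeat this for the safety objective or endpoint.
- **Time to first event.** SAP 7.6 derives it as "Study Evaluation- First AE occurrence date".

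**The concern.** Safety is a primary objective and sets the sample size. Events from the day of surgery onward are counted, but only in people already known to have kept the implant for 3 months. The selection is partly tied to a safety outcome: Protocol Table 5 makes Holger grade 4 (removal for infection) reportable, although that grade is worded for a skin-penetrating implant, and removals for other reasons need not be adverse events.

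A reader of the endpoint, the curve or the tables would take the early results as applying to everyone implanted, particularly since both documents say explanted subjects are included. Unlike sampling error, a selection of this kind does not shrink with more subjects and is not reflected in the 95% confidence interval.

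**Working it through.** **1. Can an early explant reach the safety result?** Take a subject explanted at week 6.

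| Step | Source | Result |
|---|---|---|
| Has or has had the implant | Protocol 9.3, first criterion | met |
| Had it for at least 3 months | Protocol 9.3, second criterion | not met |
| All criteria required | Protocol 9.2 | not eligible |
| FAS requires eligibility | SAP 7.1.3 | not in the FAS |
| Events in weeks 0 to 6 | Protocol 10.1, 13.3 | would have been in the window, but never counted |

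No section brings this subject back. It follows that the SAP 7.6 variable for time to explant cannot be under 3 months for any FAS subject, and that no FAS subject can leave the Kaplan-Meier risk set through explant before month 3.

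**2. The plan's own precision (Protocol 13.1: 14%, n = 72, 95%).** Plain normal half-width: 1.96 × √(0.14 × 0.86 / 72) = 8.0 points. With continuity correction, add 1/(2 × 72) = 0.7, giving 8.7 points and an interval of 5.3% to 22.7%, which rounds to the stated ±9 (5% to 23%). Enrolment: 72 / 0.75 = 96, about 100.

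**3. Illustrative size.** Let f be the share of implanted subjects excluded as early explants and q the proportion of them with a related event. Neither is in the documents; both are assumed. With 14% among those included, the all-implanted proportion is f × q + (1 − f) × 0.14, so the understatement is f × (q − 0.14).

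| f (assumed) | q = 0.5 | q = 1 |
|---|---|---|
| 1% | 0.01 × 0.36 = 0.4 points | 0.01 × 0.86 = 0.9 points |
| 3% | 0.03 × 0.36 = 1.1 points | 0.03 × 0.86 = 2.6 points |
| 5% | 0.05 × 0.36 = 1.8 points | 0.05 × 0.86 = 4.3 points |

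At q = 14% the difference is zero, and below that it reverses. Even with q = 1, f would have to be 0.09 / 0.86 = 10.5% before the shift equalled the planned 9 points.

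**4. What bounds would look like.** With 10 events in 72 subjects (13.9%) and k early explants not included, the bounds are 10/(72 + k) and (10 + k)/(72 + k):
- k = 1: 10/73 to 11/73, or 13.7% to 15.1%
- k = 3: 10/75 to 13/75, or 13.3% to 17.3%

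This treats the endpoint as a subject-level proportion. The event-rate form, which also uses exposure time, is not quantified here.

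**5. Time to first event.** Assume an event at month 1 and an evaluation at month 24. Counting from implantation, as in Protocol 13.3, gives 1 month. The SAP 7.6 formula gives 24 − 1 = 23 months. The earlier the event, the longer the derived time.

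**The case against.** **The restriction is disclosed.** It is in the synopsis, in Protocol 9.3 and in the aim in both documents, and the FAS definition points to it. This stands against any reading that the plan conceals the restriction. What remains is that the condition is not carried to the safety objective, endpoint, curve and tables.

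**The effect is probably small and its direction unproven.** This stands too. A reader might infer that the planned adverse event proportion is materially biased downward. The documents do not support that: they give no early-explant rate for this device and no event proportion among early explants. The 15.2% loss in Protocol 13.1 is for percutaneous implants in children and cannot serve as f. The series in Protocol 5.1 with no major complications in over 100 patients is reported without a follow-up time and does not bound f either.

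**The criterion may mean time since implantation.** The wording of 9.3 and the reference to implant duration in the aim point to retention. If time since implantation was meant, the rewording below settles it.

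**The screening log will show them.** Partly. Sites' logs identify explanted patients (Protocol 10.2), and a reason for failure is recorded (9.2). But the table in SAP 7.1.1 is by criterion, early explants and recent implants fail the same one, and nothing links the count to the safety result.

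**The amendment is more than one line.** Fair. FAS and PPS share one eligibility list (SAP 5.2, 7.1.3), the synopsis must change as well, and Protocol 15.5 requires IRB review.

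**Conclusion.** The point holds as a matter of definition. Primary safety estimates for months 0 to 3 describe subjects whose implant lasted at least 3 months, and the endpoint, curve and tables do not say so. This needs no numerical assumption; it rests on reading the second criterion of Protocol 9.3 as time with the implant.

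The size is unknown. If early explants are rare (1% to 3%, assumed) and half to all of them had a related event (assumed), the overall proportion is understated by 0.4 to 2.6 points, which is small against ±9. It does not follow that explanted subjects as a group are missing: those who kept the implant for 3 months or longer are included.

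The time-to-first-event formula is a separate error and does not depend on the 3-month rule. As written it does not measure time from implantation, and it conflicts with Protocol 13.3.

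**What to change.** **Preferred.** For the safety FAS, define the criterion as at least 3 months since implantation, whether or not the implant is still in place, so that consented early explants enter by chart review. Do not waive the present rule for explanted subjects alone, because entry would then depend on the outcome. Keep the current criterion for the PPS. Align the synopsis and sections 5.1 and 9.3 of the Protocol with sections 3, 5.2 and 7.1.3 of the SAP.

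*Cost.* An IRB-reviewed amendment and a few more consents and chart reviews, with no added visits: sites already log and contact all implanted patients (Protocol 10.2), and chart-only data are accepted (10.4, 10.9). Some subjects will contribute short exposure, and selection through consent remains.

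**If the criterion is kept.** State the 3-month retention condition with the safety endpoint, the Kaplan-Meier figure and the tables. Report early explants from the screening log separately from implants less than 3 months old, with best-case and worst-case bounds as in step 4 of the working. This needs SAP text and a log reason that separates the two groups.

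**Separately.** In SAP 7.6, derive time to first adverse event as first event date minus implantation (procedure) date, with subjects without an event censored at the last available follow-up. This is a correction to the SAP text and brings it into line with Protocol 13.3.

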9.4. Exclusion Criteria

- Subject has implant but is unable or unwilling to perform audiologic testing
- Subject is currently participating in another clinical study and has not been approved for concurrent enrollment by the Study Sponsor

10. Study Procedures

Prior to enrolling subjects, the Study Investigator and associated study personnel will undergo study-related training. All training will be documented and maintained in the study files.

After signing the IC and Research Authorization Forms, subjects will be screened for eligibility of the Inclusion/Exclusion criteria, which will be documented on the Inclusion/Exclusion Criteria Case Report Form (CRF).

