9.2. Subject Enrollment

All subjects will be screened for study eligibility. A qualified member of the investigational site's research team will review the inclusion and exclusion criteria to screen each subject. Subjects will be considered enrolled into the study when they have both:

- Been informed of the study design, objectives, risks and benefits
- Confirmed interest in participation by signing an IC and Research Authorization Forms

A Log of subjects treated with Sophono at each site will be reviewed for eligibility criteria. Any subject who currently has or who has had the Sophono implant (including those who have been explanted) may be enrolled. This means subjects implanted outside of the intended indications may have data collected as part of this study.

A Screening and Enrollment Log will be maintained for all subjects and will include information regarding subjects who have met the screening criteria and subjects who have not met the screening criteria (screen-fail). For screen-fail subjects, a reason for failure will be noted (e.g., patient declined participation, eligibility criterion not met, etc.).

To be enrolled in this study, subjects must meet **ALL** of the inclusion criteria and **NONE** of the exclusion criteria:

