10.4. Subject Consent

Prior to study enrollment and before any study visits are initiated, all subjects must document their consent by signing an IC and Research Authorization Form. The Study Investigator or his/her authorized designee will conduct the informed consent process during which the subject will have the opportunity to ask questions and receive answers about the study. Subjects will be made aware that the study includes a medical chart review, as well as an in-office follow-up visit, and they should be willing to comply with the study requirements to be available for study visits. If they decide not to come in for the in-office follow-up visit the data from the medical chart review will still be used in data analysis.

A copy of the signed IC and Research Authorization will be provided to the subject, and the original signed version will be retained in the site's study files. The site will record the date of consent in the CRFs.

Obtaining data from a subject's medical chart or a follow-up visit without obtaining informed consent is a protocol violation and is to be recorded in the Protocol Deviation CRF and reported to the Sponsor, as well as the respective IRB/IEC as soon as possible, **but no later than five (5) working days after the event occurred, or sooner if required by the IRB/IEC.**

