10.9. Subject Withdrawal or Discontinuation

If a subject is consented but subsequently decides to withdraw from the study before coming in for the prospective data collection visit, the subject will be considered to be withdrawn from the study, and the reason will be captured on the Study Exit CRF.

Subjects who are unresponsive after a minimum of 3 attempts to contact them by phone or other means for their prospective data collection visit will be considered lost to follow-up. The types of attempts (phone, email, text, mail) will also be captured on the Study Exit CRF. Note: retrospective safety data collected may still be used in the study.

11. Risks and Benefits

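### The audiologic-testing exclusion filters implanted subjects out of the primary safety set, although safety does not need audiometry and the effectiveness set already handles testing

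*Protocol*

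**What the plan says.** Protocol 9.4, repeated in the synopsis, lists as an exclusion "Subject has implant but is unable or unwilling to perform audiologic testing". Protocol 9.2 gives it study-wide force: "To be enrolled in this study, subjects must meet ALL of the inclusion criteria and NONE of the exclusion criteria".

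SAP 7.1.3 defines two sets. The FAS takes consented, enrolled patients who "fulfill the inclusion and exclusion criteria. The FAS will be used to evaluate the primary safety endpoint". The PPS, used for effectiveness and the secondary endpoints, takes those who "fulfill the inclusion and exclusion criteria, and perform prospective activities".

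Protocol 6.2.1.1 and SAP 7.10.1 assess primary safety through retrospective surgical chart review and the prospective ENT exam. Explanted subjects are eligible (Protocol 9.3). The clinic visit is planned only for subjects still implanted (Protocol 7), so explanted subjects supply chart data alone.

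On subjects who do not attend, Protocol 10.4 first says that "they should be willing to comply with the study requirements to be available for study visits" and then: "If they decide not to come in for the in-office follow-up visit the data from the medical chart review will still be used". Protocol 10.9, after the loss-to-follow-up rule, notes more weakly that "retrospective safety data collected may still be used in the study". Eligibility is assessed after consent is signed (Protocol 10 and 10.1).

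**The concern.** The first primary objective is implant safety in people who have or have had the implant. A criterion that serves the hearing tests decides which currently implanted people count towards it. An implanted patient who agrees to chart review but cannot or will not be tested contributes no safety data, even if the chart holds a full AE history.

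The filter could be linked to the outcome. All audiometric testing includes an aided part (Protocol 10.1), and the processor is held magnetically through the skin over the implant (Protocol 8.1). Reportable events include pain, pressure, swelling and skin necrosis (Protocol Table 5), and such events could make someone unable or unwilling to wear a processor for testing. Inability may also arise in young children; SAP 7.10.5 plans a pediatric APHAB table, so children are expected.

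Two things are at stake: an AE proportion shaped by selection that a larger sample would not remove, and FAS membership that may depend on when a refusal is voiced and on how each of up to 15 sites applies the rule.

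**Working it through.** **1. Does the exclusion reach the safety analysis?**

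- An implanted subject who cannot or will not be tested meets an exclusion (Protocol 9.4).
- Enrolment requires that no exclusion is met (Protocol 9.2).
- The FAS requires the criteria to be fulfilled, and it is the only set used for primary safety (SAP 7.1.3).

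Such a subject therefore contributes nothing to primary safety.

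**2. Is the exclusion needed there?** Neither safety source requires an audiogram. For effectiveness, the PPS already requires the prospective activities. The plan also accepts chart-only safety data from explanted subjects and from those who do not attend (Protocol 7, 9.3, 10.4).

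**3. The plan's own precision.** Inputs from Protocol 13.1: p = 0.14, n = 72, 95% confidence.

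- Wald half-width: 1.96 x sqrt(0.14 x 0.86 / 72) = 8.01 points.
- With continuity correction: 8.01 + 100/(2 x 72) = 8.01 + 0.69, or 8.71 points before rounding of the parts. The interval is 5.3% to 22.7%, which rounds to the stated 5% to 23%.
- Dropout: 72 / 0.75 = 96, stated as approximately 100.

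The figures reproduce. The point concerns who is counted, so no sample size changes.

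**4. Possible size of the selection effect.** The documents give neither the excluded share f nor its AE risk, so both are assumptions: f from 5% to 30%, and a risk ratio RR from 0.5 to 3 relative to the included set as a whole (tested implanted plus explanted). With 14% taken as the proportion in the included:

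Overall = 14% x (1 - f) + 14% x RR x f

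| f | RR 0.5 | RR 1 | RR 1.5 | RR 2 | RR 3 |
|---|---|---|---|---|---|
| 5% | 13.65% | 14.0% | 14.35% | 14.7% | 15.4% |
| 10% | 13.3% | 14.0% | 14.7% | 15.4% | 16.8% |
| 20% | 12.6% | 14.0% | 15.4% | 16.8% | 19.6% |
| 30% | 11.9% | 14.0% | 16.1% | 18.2% | 22.4% |

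The error in the reported proportion is 14 x f x (1 - RR) points. At f = 30% this is +2.1 points for RR = 0.5 (overstatement) and -8.4 points for RR = 3 (understatement).

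**5. The consent boundary.** Take two consented implanted subjects with the same chart. One declines testing at eligibility screening, meets the exclusion and leaves the FAS. The other passes screening, declines a week later, and keeps chart data in the analysis under Protocol 10.4. No passage says when willingness is judged. Protocol 9.2 adds to this by treating a subject as enrolled on being informed and signing, while also requiring that no exclusion is met.

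**The case against.** Three stronger readings are tempting, and the documents do not support them.

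*The safety set is enriched for willing device users.* The criterion concerns testing, not use. Sites hold both test processors, so an implanted patient who no longer wears the device but accepts testing is eligible. Explanted subjects, who are no longer users, enter without a testing requirement.

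*The AE proportion is biased downward.* Removing reluctant implanted subjects raises the explanted share of the FAS. If explanted subjects carry many device-related events, that pushes the proportion up. Excluded subjects could have more events than tested implanted subjects and still fewer than the included set as a whole. A range that considers only raised risk in the excluded would be one-sided. The 14% is itself a literature-based planning figure for any AE.

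*Section 9.4 contradicts 10.4 and 10.9.* Section 10.4 asks for willingness to attend before it keeps the chart data of those who then do not come, and 10.9 deals with consented subjects who later withdraw or cannot be reached. Read together, willingness at entry and retention afterwards are coherent. What stays unresolved is the subject who has signed consent and refuses before eligibility is settled.

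Two further defences have weight. Screen failures are logged with reasons (Protocol 9.2), and SAP 7.1.1 tabulates screening by criterion, so the number excluded should be visible. That shows the filter's size but does not recover the AE data. Also, implanted subjects without the ENT exam miss skin grading and direct questioning, so adding them could itself lower the AE proportion. This is a real cost, but one the plan already accepts for non-attenders, and separate reporting by ascertainment exposes it.

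**Conclusion.** The concern holds as a selection problem of unknown direction. An effectiveness-testing criterion governs entry of implanted subjects to the primary safety set, does not govern explanted subjects, and is not needed for either analysis. Under the assumed shares and risk ratios, the reported proportion could be anywhere from 2.1 points too high to 8.4 points too low, with no bias at RR = 1. At worst this is close to the stated +/-9 points, which covers sampling error only. These are illustrative bounds, not estimates.

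Separately, the FAS status of a consented implanted subject who declines testing before eligibility is confirmed is not settled. The change should be made; it affects who is counted and leaves the safety sample size as planned.

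**What to change.** 1. In Protocol 9.4 and the synopsis, make ability and willingness to be tested a condition of the audiology visit and the PPS only. Allow consented implanted subjects who cannot or will not be tested to enter for chart review, and for the ENT exam if willing, and count them in the FAS.
2. In SAP 7.1.3, state that declining testing, before or after eligibility screening, does not remove a consented subject from the FAS.
3. Reconcile Protocol 10.4, which says chart data will be used, with 10.9, which says only that they may be, and align both with item 2.
4. Report the AE proportion overall, by ascertainment (chart only versus chart plus ENT exam), and by implanted versus explanted status.

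The cost is an amendment to one criterion, a sentence in the SAP, aligned wording in two protocol sections, and extra rows in the safety table. No new procedure is needed, because chart review is already planned for all consented subjects. The downsides are less complete AE ascertainment in chart-only implanted subjects and a larger difference in size between the FAS and PPS.
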